# 3. Study Design

The study is designed as a single-site, non-randomized, single-arm pilot study of the oral TPOR agonist eltrombopag (EPAG) in Diamond-Blackfan anemia (Figure 3) to test the hypothesis: *eltrombopag improves the production of red blood cells in Diamond-Blackfan anemia patients.* The primary endpoint (see §8.2) is measured at 6 months (24 weeks ± 14 days). Subjects who cannot tolerate the medication or fail to respond by the primary endpoint will be taken off study drug. Subjects who *respond* at the primary endpoint (hemoglobin increase of 1.5 g/dL or more and/or transfusion independence for the previous 8 weeks, see §8.2.1) will be able to continue EPAG on the extension part of this protocol for an additional 3 years. During the 3-year extension phase, subjects will remain on the same dose of EPAG until they reach a *robust response* (defined as hemoglobin ≥10 g/dL in the absence of transfusions for more than 8 weeks, see §8.2.1). Drug dose will then be tapered slowly to the lowest dosage that maintains a stable hemoglobin (≥ 10 g/dL) and eventually discontinued if possible (per §5.3), until they meet off study criteria (see §8.6), or the study is closed. Drug will be restarted during extension if robust response is lost (*i.e.* hemoglobin falls below 9 g/dL).

Up to 30 subjects (18 for Stage 1 & 12 for Stage 2) will be screened to accrue 25 eligible subjects for this study.

[figure not shown]

Figure 3: Study enrollment and treatment schema

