#### 4. Eligibility Assessment

#### 4.1. Inclusion criteria

In order to be participate in this study, individuals must meet all of the following criteria:

- 4.1.1. Diamond-Blackfan anemia defined as anemia presenting on or before the third year of life with reticulocytopenia and greatly reduced or absent bone marrow erythroid precursors, supported by, but not requiring either:
  - familial history
  - gene mutation testing demonstrating a known disease-causing mutation or a mutation of disease-associated gene in combination with clinical characteristics of DBA

Patients with late-onset DBA (diagnosed after the third year of life) may also be included if gene mutation testing confirms a disease-causing mutation as above.

- 4.1.2. Clinically-significant anemia as defined as either:
  - hemoglobin less than 9.0 g/dL
  - red cell transfusion of at least 2 units PRBC for adults or 30 cc/kg for children (whichever is less) in the eight weeks prior to study enrollment
- 4.1.3. Relapsed and/or steroid-refractory or intolerant of systemic corticosteroids
- 4.1.4. Age  $\geq$  2 years
- 4.1.5. Weight  $\geq$  12 kilograms
- 4.1.6. Residence within the United States of America or territories, or able to reside within the US or its territories while on drug during trial participation

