## 5.7. Permitted supportive care

- Transfusion supportive care (e.g., blood and platelets) as clinically indicated.
- Iron chelation therapy (e.g. deferasirox, deferoxamine, deferiprone) ongoing at the time of enrollment will be continued, titrating and/or discontinuing according to established standards of care.
- Estrogens or combination oral contraceptives as indicated for uterine bleeding.
- Prophylactic antibiotics and antivirals as clinically indicated.
- The PI should be informed about all medications initiated after starting treatment with EPAG.

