#### 8.2. Endpoints

# 8.2.1. Primary endpoint

Primary efficacy endpoint will be the proportion of drug responders at 6 months. Best response (robust or not) will be noted, regardless of when it is achieved; however, for protocol purposes, primary response will be assessed according to patient status at the time of the 6-month primary endpoint assessment. Time-to-response will also be measured according to the time from eltrombopag initiation to the first time the patient met criteria for response.

*Response* to treatment will be defined by one or more of the following:

- Erythroid response for subjects with a pretreatment hemoglobin less than 9 G/dL will be defined as an increase in hemoglobin by >1.5 G/dL from enrollment baseline, *and/or*
- a reduction in the units of PRBC transfusions by at least 50% during the eight consecutive weeks prior to response assessment compared with the pretreatment transfusion number in the previous 8 weeks.

*Robust response* to treatment will be defined both:

- Stable hemoglobin (two consecutive measurements at least 2 weeks apart) greater than 10 g/dL, *and*
- Transfusion independence for the previous 8 weeks

For sub-analyses, *transient response* to treatment (robust or otherwise) is defined as any response meeting the respective criteria above within the first 6 months that is subsequently lost and not regained prior to the 6-month primary endpoint assessment. While note will be made of such patients, for the purposes of primary response analysis, these patients will be considered *non-responders* along with patients who fail to meet the above response criteria.

Primary safety endpoint will be the toxicity profile assessed at 6 months using CTCAE criteria.

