*Transfusion Units:* In pediatric patients, the administration of red blood cell transfusions is typically weight based, typically 10-15 mL/kg, reaching a maximum of one bag of packed erythrocytes (300-350 mL). For protocol purposes, a "transfusion unit" for pediatric patients is 15 mL/kg of packed erythrocytes. For adults and pediatric patients weighing approximately 20 kg or greater, "units" will be measured in bags. Where ambiguity exists, the clinical record shall be reviewed to determine the intent of the ordering physician as to whether dosing was per-bag or on a weight basis. It will be the responsibility of the PI to adjudicate any remaining ambiguity. Transfusions administered for non-disease indications (e.g., trauma, acute blood loss, perioperative hemostasis, *etc.*) will be noted, but not included in statistical and response considerations.

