#### 8.3. Sample size

Because the efficacy of eltrombopag in this patient population is unknown, we would like to reject the treatment as quickly as possible with a small number of patients if the treatment is not effective. We will use the Two-Stage Minimax Design outlined in Table 1 of Simon (89) with a response probability of 10% or less to terminate the treatment and the hypothesized actual response probability of 30% or more. The sample size is determined by testing the null hypothesis  $H_0$ :  $p \le 10\%$  versus the alternative  $H_1$ :  $p \ge 30\%$  at a significance level of 0.05 and a power of 0.8. At the first stage, we will accrue 15 subjects, and the null hypothesis will be accepted if no more than 1 subject responds to the treatment at 6 months. If 2 or more subjects respond to the treatment at 6 months at the first stage, then we will accrue an additional 10 subjects, bringing the total number of subjects to n = 25. The null hypothesis of  $p \le 10\%$  will be accepted if the total number of responders at 6 months is 5 or less. These efficacy thresholds were selected as being clinically relevant for the avoidance of alternative therapies such as hematopoietic stem cell transplant. Given an observed screening fail rate of 16.7%, we will recruit 30 patients (18 in the first phase, 12 in the second phase) to ensure that the target of 25 eligible patients is reached.

With an incidence of approximately 1 in 100,000-200,000 live births (18), and an expectation of approximately 25-35 new diagnoses a year in the USA, of which 15-20 will likely prove refractory to treatment, and in conjunction with recruitment through patient networks and ongoing natural history studies at the NIH (see §10.1), accrual is projected to take 2.5-3 years.

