#### Table 8: Attribution of adverse events

Relationship	Attribution	Description
Unrelated to investigational	Unrelated	The AE is clearly NOT related to the intervention
agent/intervention 	Unlikely	The AE is doubtfully related to the intervention
Related to investigational agent/intervention 	Possibly	The AE may be related to the intervention
	Probably	The AE is likely related to the intervention
	Definitely	The AE is clearly related to the intervention

**NOTE:** AEs listed as 'possibly, probably, or definitely' related to the investigational agent/intervention are considered to have a suspected 'reasonable causal relationship' to the investigational agent/intervention (ICH E2A).

In view of the underlying disease (Diamond-Blackfan anemia), all patients will enter the study with abnormally low blood counts that would meet criteria for grade 2 and more commonly higher toxicity. Also, platelet and red blood cell counts will be impacted by frequent transfusions. Therefore, AEs regarding low hematologic lab values, including thrombocytopenia or platelet-transfusion dependence, anemia or red cell transfusion dependence, neutropenia, lymphopenia, or leukopenia are not evaluable and will not be recorded.

Non-hematologic abnormal laboratory findings used to evaluate the safety of this protocol regimen will include any change from laboratory assessments done prior to first dose of study medication that result in a progression to grade 3 or 4 laboratory toxicity or are characterized by any of the following:

- Results in discontinuation from the study
- Is associated with clinical signs or symptoms
- Requires treatment or any other therapeutic intervention
- Is associated with death or another serious adverse event, including hospitalization
- Is judged by the Investigator to be of significant clinical impact
- If any abnormal laboratory result is considered clinically significant, the investigator will provide details about the action taken with respect to the test drug and about the patient's outcome.

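### The hemoglobin arm of the primary response carries no transfusion-free condition, so a recent red cell transfusion can be scored as a drug response

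*Combined protocol and SAP*

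**What the plan says.** Section 8.2.1 defines response by one or both of two criteria. The first applies to subjects with pretreatment hemoglobin below 9 g/dL and "will be defined as an increase in hemoglobin by >1.5 G/dL from enrollment baseline". The second is a cut of at least half in red cell units over the 8 weeks before assessment, compared with the 8 weeks before treatment. Only robust response adds "Transfusion independence for the previous 8 weeks" and a second hemoglobin value.

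Other sections bear on this:

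- Section 4.1 admits subjects through low hemoglobin or through "red cell transfusion of at least 2 units PRBC for adults or 30 cc/kg for children" in the 8 weeks before enrollment.
- Section 5.7 permits "Transfusion supportive care (e.g., blood and platelets) as clinically indicated".
- Section 9.2.2, in the text after Table 8, accepts that "platelet and red blood cell counts will be impacted by frequent transfusions" and for that reason does not record low counts as adverse events.
- The transfusion-units paragraph of 8.2.1 says that transfusions for non-disease reasons "will be noted, but not included in statistical and response considerations".
- Section 8.3 sets 10% and 30% as the two response rates and gives this basis: "These efficacy thresholds were selected as being clinically relevant for the avoidance of alternative therapies such as hematopoietic stem cell transplant".
- Section 3, citing 8.2.1, words response differently: "hemoglobin increase of 1.5 g/dL or more and/or transfusion independence for the previous 8 weeks".

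**The concern.** A hemoglobin value taken soon after a transfusion measures the transfusion as well as the marrow. The plan recognises this elsewhere. The taper trigger in section 5.3 requires more than 8 weeks without transfusion, and the platelet thresholds in section 5.2 refer to untransfused counts. The hemoglobin arm of the primary endpoint has no such condition, and no section ties the scored 6-month blood count to time since transfusion. Section 6.4 has transfusion records reviewed at that visit but does not link them to the hemoglobin criterion. Non-disease transfusions are set aside when response is judged, yet they raise the scored hemoglobin too.

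The trial has one arm, so no control group would reveal how often the definition is met without any drug effect. Responders produced by transfusion would count toward the 2 of 15 and 6 of 25 needed to go on and to declare efficacy.

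**Working it through.** **1. The plan's own design.** Inputs from section 8.3: 15 subjects in stage 1, stop if 1 or fewer respond; 25 in total, accept the null if 5 or fewer respond. With response probability p,

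P(declare efficacy) = Σ over x = 2 to 15 of P(Bin(15, p) = x) × P(Bin(10, p) ≥ 6 − x).

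At p = 0.10 this is 0.0328, and the chance of stopping after stage 1 is 0.549. At p = 0.30 it is 0.8017. The stated 0.05 and 0.80 are met, and a search confirms 15/25 as the minimax design. The sample size is right for its inputs.

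**2. Sensitivity to the response rate without drug effect.** The same formula gives:

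| Response rate without drug effect | P(declare efficacy) |
|---|---|
| 5% | 0.1% |
| 10% | 3.3% |
| 11.05% | 5.0% |
| 15% | 15.9% |
| 20% | 37.9% |

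The margin above 10% is about one percentage point.

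**3. How much the hemoglobin arm could add (illustration; every input is assumed).** Take a regularly transfused subject with no drug effect. Hemoglobin falls in a straight line from a post-transfusion peak to a trough of 7.5 g/dL, a swing of s. The baseline and 6-month values fall at independent random points of the cycle. A rise above 1.5 g/dL then has probability (1 − 1.5/s)² / 2 if s exceeds 1.5, and zero otherwise:

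- s ≤ 1.5: 0
- s = 2: 0.25² / 2 = 3.1%
- s = 2.5: 0.40² / 2 = 8.0%
- s = 3: 0.50² / 2 = 12.5%

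The entry condition of this arm does not bind here. A baseline more than 1.5 below the peak is below 7.5 + s − 1.5 = 6 + s, which is at most 9 for s up to 3.

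A simulation adds explicit intervals (mean 2–4, 3–5, 4–5 or 4–6 weeks, SD 0.5 week) and the transfusion arm. In it, the hemoglobin arm adds 3.2 to 13.4 points to the transfusion arm at swings of 2 to 3 g/dL, and 0 at 1 or 1.5 g/dL.

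**4. The opposite direction.** In the same cycle, the share of time at or above 9 g/dL is (7.5 + s − 9)/s: 25% at s = 2 and 50% at s = 3. A baseline drawn then removes the subject from the hemoglobin arm. A baseline raised by transfusion but still below 9 makes a true rise harder to show.

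**5. The other arm.** In the same simulation, the 50% reduction criterion alone is met without drug effect in about 1.4%, 8.5%, 15.3% and 20.5% of regularly transfused subjects for the four interval ranges. With either arm allowed (swing 2 to 3), the totals are 4.5–14.1%, 11.8–20.7%, 18.6–27.1% and 23.9–34.0%. With an 8-week transfusion-free condition on the hemoglobin arm, the total equals the transfusion arm alone in every case.

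**6. Price in power.** If the scored rate under an active drug fell from 30% to 27%, power would go from 80.2% to 69.9%. At 25% it would be 61.6%.

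**The case against.** The strongest reply is that no harm is demonstrated. The documents give no share of regularly transfused subjects, no hemoglobin swing, no interval and no sampling time. With swings of 1.5 g/dL or less the hemoglobin arm adds nothing, and a transfused baseline can work against response. All of this stands, and it limits the claim about size.

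Second, the two response criteria parallel the two entry routes. The intent may have been hemoglobin for anemic entrants and units for transfused ones. That is plausible, but 8.2.1 accepts either criterion in any subject with a low pretreatment value, and such a subject may also be transfused. If the restriction was intended, it is not written.

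Third, 10% is a clinical-relevance threshold below which treatment is abandoned, and this is a legitimate use of a null rate in a pilot. A reader might infer that section 8.3 is wrong for lack of a historical rate. The documents do not support that; at most a caveat is missing.

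Fourth, robust response is recorded separately and transfusion records are reviewed, so a transfusion-free result can be recovered. True, but the go/no-go count uses ordinary response.

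Finally, the 50% reduction arm may be the larger source of background. Under the assumed cycle this is often so, and changing the hemoglobin arm does not cure it.

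**Conclusion.** The gap holds on the text: the primary hemoglobin criterion can be met by transfused blood, and nothing in the protocol prevents it. It should be fixed, because the primary count can be wrong even when the rule is applied faithfully.

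The consequence for error rates is conditional. The exact figures in steps 1 and 2 need no assumption beyond independent subjects with a common response rate. The addition of about 3 to 13 points rests wholly on an assumed cycle, applies only to regularly transfused subjects, and is zero at swings of 1.5 g/dL or less. A reader might infer that the trial's type I error exceeds 5%. The documents do not show this: it would require a response rate without drug effect above about 11%, and they give no such rate in either direction. Nor does the fix guarantee the stated level, given the background of the other arm.

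The mismatch between sections 3 and 8.2.1 is a separate inconsistency and adds no weight to the background question. It does have an effect: a subject whose units fall by 60%, who is still transfused and has no hemoglobin rise, is a responder under 8.2.1 but not under section 3.

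**What to change.** (a) In 8.2.1, for the primary efficacy analysis, count the hemoglobin arm only if no red cell transfusion, for any indication, was given in the 8 weeks before the scored 6-month value. Assess subjects transfused in that window on the transfusion arm, where the exclusion of non-disease transfusions still applies. Do not substitute an older hemoglobin value, since 8.2.1 scores status at the 6-month assessment and treats lost responses as non-response. List subjects whose only transfusion in the window was for a non-disease reason, and show the result with and without them. Report responders by arm met. If responses have already been analysed, present this as a sensitivity analysis.

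(b) Optionally, note in 8.3 that the type I error is conditional on a response rate without drug effect of at most 10%.

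(c) Separately, reconcile the response wording of section 3 with 8.2.1. Section 6.5 ties extension entry to 8.2, and section 8.6 lists lack of response by week 24 as an off-study criterion. The protocol should say whether these follow the analysis definition. No rule for continuing drug is proposed here.

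Cost: no new data, because blood counts and transfusion records are already collected. Section 6.4 lists the record review only if records are available, but the transfusion arm depends on the same records. The drawback is a lower scored response rate, with the power loss shown in step 6. A previously transfused subject with 8 transfusion-free weeks already meets the 50% criterion, so the hemoglobin arm would in effect serve subjects who enter untransfused.

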- Pregnancy test (blood or urine hCG in women of child bearing potential)
- Bone marrow aspiration and core biopsy, to be stained for standard morphologic analysis and quantitation of cellularity with hematoxylin and eosin, and special stains to assess reticulin and collagen, iron, primitive stem and progenitor cells via CD34 immunohistochemistry, and other lineage-specific or special stains as indicated to classify any abnormalities
- Bone marrow chromosomal analysis via standard cytogenetic techniques
- Pediatric consult for patients under 18 years of age
- Electrocardiogram (EKG)
- Review of red blood cell transfusion records for the 8 weeks prior to study entry

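### The transfusion leg of the primary response compares two single 8-week counts, so a subject transfused about every 4.5 to 6 weeks, or irregularly, can be scored as a responder with no change in transfusion rate

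*Combined protocol and SAP*

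**What the plan says.** Inclusion criterion 4.1.2 can be met by hemoglobin below 9.0 g/dL or by "red cell transfusion of at least 2 units PRBC for adults or 30 cc/kg for children (whichever is less) in the eight weeks" before enrollment. For children, Section 8.2.1 sets the unit so that 30 cc/kg equals 2 units: a transfusion unit "for pediatric patients is 15 mL/kg of packed erythrocytes".

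The transfusion leg of the primary response in 8.2.1 is "a reduction in the units of PRBC transfusions by at least 50% during the eight consecutive weeks prior to response assessment". The baseline is a single count of the same length, since the reduction is judged "compared with the pretreatment transfusion number in the previous 8 weeks". The hemoglobin leg and the transfusion leg are alternatives, so either one alone makes a responder. The only pretreatment transfusion history that the plan collects is in 6.1: "Review of red blood cell transfusion records for the 8 weeks prior to study entry". On study, 5.7 allows "Transfusion supportive care (e.g., blood and platelets) as clinically indicated", with no fixed trigger or interval.

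Time to response in 8.2.1 runs to the "first time the patient met criteria for response", and best response counts whenever it occurs.

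Section 3 summarizes response differently. There the transfusion alternative is independence from transfusion over the preceding 8 weeks, not a halving, although it points to 8.2.1.

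Section 8.3 tests a 10% response rate against 30% with 15 + 10 subjects. It chooses these rates for clinical relevance and makes no stated allowance for chance response.

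**The concern.** An 8-week window holds only one to three transfusion visits for many schedules. When two such counts are compared, the position of the window alone can move a subject from 2 to 1, which is exactly a 50% cut. This needs no change in hemoglobin, no deferred unit and no drug effect.

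Selection can add to it. If a subject needs two visits in the window to enter, those whose window happened to hold two are admitted, and that high count becomes their baseline.

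The trial has one arm, so no control group would show how often this happens. If it happens often enough across the 25 subjects, the test against 10% no longer has its planned error rate. The 6-month response also decides who may continue into the extension.

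**Working it through.** **The plan's own design.** For response rate p, the probability of declaring success is the sum over x ≥ 2 of Bin(x; 15, p) × P[Bin(10, p) ≥ 6 − x]. This gives 0.033 at p = 0.10 and 0.802 at p = 0.30. A search over designs returns the same minimax choice (15/25, continue on 2 or more, success on 6 or more). The design is reproduced. The documents give no chance-response figure to reproduce.

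**Exact case.** Take an evenly spaced schedule with interval k between 4 and 8 weeks, and treat the positions of the two windows as independent. A window holds 2 visits with probability f = 8/k − 1, and otherwise 1.

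- Chance of going from 2 to 1: f(1 − f).
- The same, given that two visits were needed to qualify: 1 − f.
- k = 4.5: f = 0.778, giving 0.17 and 0.22.
- k = 5: f = 0.6, giving 0.24 and 0.40.
- k = 6: f = 0.333, giving 0.22 and 0.67, but only a third of such subjects qualify.
- k of 4 weeks or less: zero.

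**With ordinary irregularity.** Simulation of 200,000 subjects per setting: gamma intervals, CV 20% (assumed), random phase, unchanged rate, baseline weeks −8 to 0, follow-up weeks 16 to 24, response if the follow-up count is at most half of baseline. The second and fourth columns apply when one 2-unit visit is enough to qualify. They are then almost the same as the figures with no selection.

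| Mean interval (weeks) | 8-week baseline, 2-unit visits | 8-week baseline, two single-unit visits needed | 24-week averaged baseline, 2-unit visits |
|---|---|---|---|
| 2.6 | 2% | 2% | 0% |
| 3 | 1% | 1% | <1% |
| 3.5 | 3% | 3% | 3% |
| 4 | 10% | 11% | 9% |
| 4.5 | 19% | 25% | 9% |
| 5 | 24% | 41% | 4% |
| 5.5 | 25% | 56% | 1% |
| 6 | 22% | 64% | 1% |

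At CV 50% with no selection, the figures at 2.6-3.5 weeks rise to about 11-17%. At 5 weeks and CV 50%, the 24-week baseline lowers 28% to 16% (2-unit visits) and 47% to 21% (single-unit visits).

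The longer baseline works because it gives fractional counts. At 5 weeks, five visits in 24 weeks average 1.67 per 8 weeks. Half of that is 0.83, so a single on-treatment visit no longer counts. At 4 weeks, six visits average exactly 2, so one visit still counts and little is gained.

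**Effect on the trial.** Putting overall chance-response rates into the two-stage formula:

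| Chance response over all subjects | P(declare success) |
|---|---|
| 5% | 0.1% |
| 10% | 3.3% |
| 15% | 15.9% |
| 20% | 37.9% |
| 24.3% | 58.5% |

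If a share w of subjects behaves like the 5-week case (24%) and the rest contribute nothing, the overall rate is 0.24w. Reaching 10% needs w = 10/24 = 42%, and reaching 15% needs w = 15/24 = 63%.

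**The case against.** The strongest reply is that the documents do not place subjects in the affected range. Their only transfusion rate, in Section 2.2, is a general one: 20 transfusions, typically within the first year of chronic transfusion. That is 52/20 = 2.6 weeks or less between transfusions, where chance response is about 2% at CV 20%. A 5.2-week interval follows only if those 20 are units given two per visit, which the text does not say. This stands: a reader might infer that an unchanged schedule is often scored as a response, and the documents do not show that.

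A reader might also blame the shared entry and baseline window. That holds only when two visits are needed to qualify. With 2-unit visits, one visit is enough, selection adds almost nothing, and the error comes from comparing two very small counts.

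A third tempting reading is that the trial has a 58% chance of false success. That is a bound requiring all 25 subjects to be near a 5-week interval. Subjects may also enter on hemoglobin alone, and at an overall chance rate of 10% the test still runs at its designed 3.3%.

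On the secondary endpoints, Section 6.4 reviews transfusion records at 3 and 6 months. The 3-month look-back covers weeks 4 to 12, all on drug. Scoring before week 8 would require earlier looks or back-dating, and the plan neither states nor excludes this. With two-weekly looks, as an assumption, 59% of unchanged 5-week subjects would meet the rule at some look, and 45% of all such subjects before week 8.

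Finally, under Section 3's wording a change from 2 to 1 would not be a response at all. What remains is that 8.2.1, the section that defines the endpoint, carries the 50% rule and can misclassify as written.

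**Conclusion.** The point holds in a limited form. As 8.2.1 is written, subjects with an unchanged transfusion rate can be scored as responders if they are transfused about every 4.5 to 6 weeks or irregularly. The chance is roughly one in five to one in four at CV 20%, and more for those who needed two single-unit visits to enter. At 3.5 weeks or less with fairly regular visits it is 1-3%.

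The consequence for the primary test cannot be fixed from the documents. It runs from no harm (overall chance response of 10% or less) to false success of 16-38% at 15-20%. All chance-response rates rest on assumed intervals, units per visit and CV. Confidence is medium. The change is worth making because it is cheap and a single-arm trial cannot detect the problem afterwards.

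**What to change.** 1. Reconcile the transfusion criterion in Section 3 (independence) with that in 8.2.1 (at least a 50% reduction).
2. If the 50% rule stands, define the baseline in 8.2.1 as average units per 8 weeks over up to 24 weeks before first dose, with at least 16 where records allow. Omit weeks on corticosteroids or androgens and scale to the weeks that remain. Exclusion 4.2.5 requires only 4 weeks off these drugs, so without the omission up to 20 of 24 baseline weeks could be on them, against 4 of 8 now. Keep the 8-week on-treatment window and report the result with the 8-week baseline as a sensitivity analysis.
3. In 6.1, extend the transfusion record review from 8 to 24 weeks.
4. For time to response and best response, do not score the transfusion leg before week 8 on drug, so that the look-back contains no pre-drug weeks.

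Expected gain at CV 20%: chance response falls from 24% to 4% at 5 weeks and from 22-25% to about 1% at 5.5-6 weeks. There is little change at 4 weeks or less (10% to 9% at 4 weeks), and the gain is smaller when visits are very irregular.

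The cost is wording in 8.2.1 and 6.1 and a longer request for records already being sought. Older outside records are harder to obtain, and some subjects will have a shorter usable baseline.
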